- Has been diagnosed with knee disorder other than osteoarthritis, post-traumatic osteoarthritis, gout, pseudo gout, or any inability to walk due to disorders unrelated to the knee (e.g., hip disorders, spinal stenosis, paralysis, hemi-paralysis)

V. STUDY PRODECURES

Patients who are undergoing total knee replacement (TKR) with [name] at Brigham and Women's Faulkner Hospital and meet all eligibility criteria will be informed about the study and asked if they would like to participate. The research assistant (RA) will screen upcoming surgeries and mail a letter describing the study to all qualifying patients to inform them of the study. If the patient has not contacted the study team within one week after this letter is mailed, the RA will call the patient by phone and ask whether the patient agrees to participate. Those who show interest will be offered the opportunity to discuss with both the RA and Principal Investigator (PI). Upon agreement, the patient's consent will be obtained and they will be randomly assigned to a treatment group using a computer-generated randomization.

A standardized mean difference of 0.90 has been reported in the previous published studies for quadriceps muscle strength between control and NMES intervention groups. This study will require 26 patients per group using this standardized mean difference, along with 80% power and the level of significance (p-value) set to 0.05. Adding in a 10% expected dropout rate, planned enrollment will be 29 patients per group for a total enrollment of 87 patients.

Approximately 2-3 months before surgery, patients will sign informed consent and will be randomly assigned to one of 3 treatment groups, to be described in detail below. Patients in all groups will receive a standardized telemedical “Pre-Hab” program (iGetBetter, Southborough, MA) to be followed in anticipation of surgery. This program includes both strengthening exercises and proprioception exercises. Prior to enrolling in the Pre-Hab program, all patients will undergo our standardized functional testing, including proprioceptive evaluation. The RA will also give each patient a live tutorial on how to use iGetBetter.

During their preoperative appointments, all patients will undergo preoperative testing to assess joint function and leg strength. Tests will measure sit-to-stand capabilities, quadriceps strength, distance walked in 2 minutes, walking speed, proprioception (balance), and range of motion.

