Patients in all groups will attend two routine follow-up visits. The first will occur one week after surgery; there patients will have their dressing changed and receive narcotic prescriptions. At the second follow-up, which will occur 2–3 months after surgery, patients will receive the functional testing described above. We will also calculate total cost of the three different treatment modalities.

Additional routine data — including postoperative complications for infection, readmission rates, and routinely collected functional outcome measures — will be recorded at this 2- to 3-month visit. For all groups, the standard of care is to administer an opioid consumption diary in which patients submit VAS scores for pain, nausea, and satisfaction. The PI will review this diary with the patient during the first postoperative visit, and then again at the second. We will measure patients' pain, both in terms of VAS scores and in terms of total pain medications consumed. Each of these measures will be used for analysis at the completion of the study.

VI. BIOSTATISTICAL ANALYSIS

We will be comparing the three separate groups in the trial to see whether there exists a statistically significant difference between them. Variables in which we are interested are all detailed in the previous section. When comparing the three branches, all analyses will be run at a type I error rate of 5%.

VII. RISKS AND DISCOMFORTS

It is possible that the iGetBetter group could have worse outcomes than the other two groups if a patient does not log into the program, or does too many (or too few) of the exercises prescribed. However, our current experience is a high compliance rate with iGetBetter exercises and good hip and knee strength and standing balance 2 months after total knee replacement. Risks associated with a web-based rehabilitation program will be minimized by closely monitoring all information recorded by the patient. If patients are recording high pain scores or not recording exercises, the PI will be notified and the RA will contact those patients.

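### Section VI tests every outcome at 5% with none declared primary and no multiplicity rule: the chance of at least one false positive over six to ten outcomes is about 17–36% (assumed correlation 0.3–0.7)

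*Combined protocol and SAP*

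**What the plan says.** The whole of Section VI (Biostatistical Analysis) is three sentences. The purpose: "We will be comparing the three separate groups in the trial to see whether there exists a statistically significant difference between them". The variables: "Variables in which we are interested are all detailed in the previous section". The error rate: "all analyses will be run at a type I error rate of 5" per cent.

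Section V (Study Procedures) supplies the variables:

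- Functional tests, done before surgery and repeated at the 2–3-month visit: "sit-to-stand capabilities, quadriceps strength, distance walked in 2 minutes, walking speed, proprioception (balance), and range of motion".
- Pain, measured "both in terms of VAS scores and in terms of total pain medications consumed".
- A diary with "VAS scores for pain, nausea, and satisfaction".
- Routine data: "postoperative complications for infection, readmission rates, and routinely collected functional outcome measures".
- Total cost of each modality.

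The paragraph on routine data, diary and pain ends: "Each of these measures will be used for analysis at the completion of the study".

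No section calls an outcome primary or secondary, names a test, picks a primary comparison, says what follows a significant three-group result, or gives a multiplicity rule. Quadriceps strength has one distinction: the sample size in Section V uses a standardized mean difference (SMD) of 0.90 for it between control and NMES. Section II (Specific Aims) lists it as one of several measures.

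**The concern.** A three-group test at 5% protects one outcome. Applied separately to six or more outcomes, with none ranked, it does not hold the chance of some false claim at 5%. A difference could be reported on whichever measure crosses 0.05, and that need not be quadriceps strength, the only measure with a sample-size basis.

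The stated expectations do not settle which result leads, because they conflict:

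- Section I calls the trial a non-superiority study.
- Section II sets out to investigate superiority, then proposes equal outcomes. It adds a value rule: outpatient therapy cost down by 50% with outcome down by no more than 10%. The same sentence goes on to rule out any loss of outcome.
- Section VII says there is no clear hypothesis on how the groups will rank.
- Section VIII expects the home-therapy control to do as well as the other two groups or better.

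With equality among the aims, there is a second risk: non-significant results may be read as showing equality, which a test for a difference cannot do.

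**Working it through.** **1. The plan's own figure.** Inputs from Section V: SMD 0.90, 80% power, level 0.05, 10% dropout.

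- Two-group normal approximation, two-sided: n = 2(1.960 + 0.842)² / 0.90² = 19.4, so 20 per group; the exact t-test needs 21.
- Three-group F-test with the extreme groups 0.90 SD apart and the third midway (assumed): f = 0.90/√6 = 0.367, which needs 25 per group, close to the stated 26.
- Dropout: 26/0.90 = 28.9, so 29 per group, and 3 × 29 = 87, as stated.

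The normal approximation also gives 26 at a level of 0.05/3 or at 90% power. The plan states 0.05 and 80%, so 26 cannot be read as a hidden multiplicity rule.

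**2. Number of outcomes.** Six functional tests. Adding VAS pain and total pain medication makes eight; adding VAS nausea and satisfaction makes ten. Total cost, infection, readmission and routine functional measures are not counted. Testing them as well could only raise the chance of a false positive.

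**3. Independence bound.** 1 − 0.95^m gives 0.265 (m = 6), 0.337 (m = 8) and 0.401 (m = 10).

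**4. Correlated outcomes.** Simulation of 40,000 trials: 3 × 26 patients, normal outcomes with equal correlation, no true effects, one F-test (2 and 75 degrees of freedom) at 0.05 per outcome. The documents give no correlation, so a range is shown. Entries are the chance of at least one false positive.

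| Outcomes | 0 | 0.3 | 0.5 | 0.7 | 0.9 |
|---|---|---|---|---|---|
| 6 | 0.267 | 0.245 | 0.212 | 0.172 | 0.112 |
| 8 | 0.335 | 0.302 | 0.258 | 0.200 | 0.125 |
| 10 | 0.400 | 0.356 | 0.297 | 0.223 | 0.131 |

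A single outcome gave 0.052, which is 5% within simulation error. A separate run of 200,000 trials gave 0.246 and 0.169 for six outcomes, and 0.355 and 0.224 for ten, at correlations 0.3 and 0.7. With the two walking measures correlated at 0.9 and the rest at 0.5, the results were 0.197 for six and 0.289 for ten.

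**5. Error under the proposed rules, one primary outcome, no true effects (400,000 trials).** Pairwise tests run only after a significant F-test (gated): 0.050. Holm on Groups 2 and 1 v Group 3: 0.046. The same two comparisons unadjusted: 0.091.

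**6. Power for Group 2 v Group 3, 26 per group.** The result depends on where the Group 1 mean lies.

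| Rule, SMD | Group 1 = Group 3 | midway | Group 1 = Group 2 |
|---|---|---|---|
| Gated, 0.90 | 0.864 | 0.813 | 0.866 |
| Holm, 0.90 | 0.822 | 0.827 | 0.868 |
| Gated, 0.80 (assumed) | 0.764 | 0.701 | 0.767 |
| Gated, 0.70 (assumed) | 0.638 | 0.576 | 0.635 |

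A single unadjusted two-sided 5% t-test has power 0.889, 0.807 and 0.697 at SMD 0.90, 0.80 and 0.70.

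**The case against.** The best defence is that quadriceps strength, control v NMES, is in effect primary: it is the only outcome and comparison with a sample size. A three-group test already holds 5% for it, and an error rate across all outcomes matters only if all are confirmatory, which the documents never say. The per-outcome protection stands, and so does the implied lead. But Section VI applies one significance criterion to all variables without ranking them. Nor do the documents call the trial exploratory: Section II speaks of superiority, and Section V plans 80% power.

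The size is also open to challenge, and this stands in part. The correlation is assumed. The sentence sending each measure to analysis follows directly on the pain measures and may cover only those, which would make eight outcomes rather than ten. For that reason the result is given as a range for six, eight and ten, with wider bounds.

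Finally, if the true aim is comparability, reading non-significance as equality is a greater danger than false differences. That stands too, and it makes the fix depend on the aim.

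Stronger readings are tempting but not supported:

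- **That the plan runs unadjusted pairwise tests.** Three per outcome would give 12% for one outcome, and at correlation 0.7 to 0.3, 36–50% for six and 44–67% for ten. Section VI describes a comparison of three groups and neither states nor rules out pairwise tests, so these figures are a worst case.
- **That the trial has no hypothesis at all.** Section VII alone suggests this; Sections II and VIII state expectations, though conflicting ones.

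**Conclusion.** The point holds. Followed as written, the plan keeps 5% for each outcome but not across them. At an assumed correlation of 0.3–0.7, the chance of at least one false positive is about 17–25% for six outcomes, 20–30% for eight and 22–36% for ten. Across six to ten outcomes the bounds run from 11% (six outcomes, correlation 0.9) to 40% (ten independent outcomes). The figures rest on one three-group test per outcome, normal data, 26 per group and no true effects.

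A reader might take these percentages as the probability that a reported significant result is false. They are not: they give the chance of any false positive when no outcome truly differs. A reader might also infer that no extra patients are needed whatever the aim. That follows only if the aim is to detect a difference of the stated size.

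**What to change.** Before outcome data are examined:

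1. Reconcile the aim across Sections I, II, VII and VIII, including how Section II's 50% cost and 10% outcome rule is to be used.
2. If the aim is to detect a difference, name quadriceps strength at the 2–3-month visit as the single primary outcome. Hold its comparisons at an overall two-sided 5% by one stated rule: either (a) a three-group test such as one-way analysis of variance, with pairwise tests only if it is significant, or (b) Holm for Group 2 v Group 3 and Group 1 v Group 3. Rule (a) is closer to Section VI's wording. The documents state neither sidedness nor a time point for the SMD, so both are proposals here.
3. Label all other outcomes secondary and report them as estimates with confidence intervals, without confirmatory claims.
4. State that a non-significant result is not evidence of equality.

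For a difference-testing aim the cost is wording only. Group 2 v Group 3 stays above the planned 80% power at the stated SMD under either rule. There is less room if the effect is smaller: at an assumed SMD of 0.80, rule (a) gives about 70–77%. Power for Group 1 v Group 3 is not established, because no effect size is stated for telemedicine. Secondary outcomes can no longer carry a claim at 5%.

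If the aim is non-inferiority, the test, margin and power must be restated, and none of these power figures applies.
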